Secondary Hypothesis: We hypothesize that the TV generated via PLV in the immediate neonatal transition phase will be highly variable.

PHASE II:

Primary Hypothesis: We hypothesize that real time PiP adjustments are feasible when utilizing a T-Piece resuscitator to provide VTV for goal TV of 4-6ml/kg that can be seamlessly transitioned in the NICU.

Secondary Hypothesis:

- i. We hypothesize that infants receiving VTV will require lower PiP, will have lower oxygen needs with improved long term pulmonary morbidities
- ii. We hypothesize that VTV will have lower complication rates as compared to PLV.

SPECIFIC AIMS:

PHASE I:

Specific Aim #1: To assess feasibility of measuring TV in the DR for preterm infants <32 weeks with need for invasive positive pressure ventilation via endotracheal tube (ETT).

Objectives:

Date 10/15/2018
Protocol Version-I

- To assess the % infants with all equipment ready(including NM3 monitor and flow sensor) in DR to measure TV
- To assess the % infants where TV was measured within 60 seconds of ETT placement and positive pressure ventilation initiation.

Specific Aim #2: To assess variability in delivered TV in the DR with PLV for preterm infants <32 weeks with need for invasive positive pressure ventilation via ETT

Objectives:

- To assess the % infants with tidal within goal of 4-6ml/kg via routine PLV
- To assess the % infants with under or over ventilation using routine PLV
- To assess changes in TV with administration of surfactant with the same pressures

PHASE II:

Specific Aim #1: To assess feasibility of providing VTV, by quickly adjusting the peak inspiratory pressures (PiP) provided via the T-Piece resuscitator based on real time TV measurements.

Objectives:

- To assess the recruitment rates and successful enrollment into the study
- To assess the % of infants with measurable TV and successful adjustment of PiP to reach goal TV
- To assess the % of infants who fail VTV and need to be switched to conventional PLV

Specific Aims #2: To compare the pulmonary mechanics and physiology during VTV, respiratory support requirements

Objectives:

- To compare TV delivered during PLV versus VTV.
- To compare FiO2 requirement during PLV versus VTV
- Evaluate PiP, mean airway pressures (Paw), peak end expiratory pressures (PEEP) and oxygen requirement during the first 48 hours between the two study arms.
- Evaluate differences in blood gas results (pH, PCO2 levels).

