Specific Aim #3: To assess complication rates and long term outcomes for infants receiving VTV versus PLV.

Objectives:

- To compare the total duration of neonatal resuscitation before reaching a stable state ready for transfer to NICU from the DR
- To record APGAR scores as a means to evaluate the ongoing resuscitation
- Compare oxygen requirements between VTV and PLV group during DR resuscitation
- To assess the incidence of complications including pneumothorax
- To evaluate for other unexpected adverse events that may be associated with VTV
- Evaluate longer term pulmonary morbidities: duration of invasive ventilation, BPD rates, and home oxygen requirements at discharge.

DESIGN AND PROCEDURE

EXPERIMENTAL DESIGN

Phase I: Phase I will be an observational, non-interventional study. All infants will receive routine resuscitation as recommended by the NRP. A flow sensor device connected to Respironics NM3 monitor (*Philips Healthcare, Eindhoven, Netherlands*), will be placed between the ETT and T-piece resuscitator to measure breath to breath tidal volume. Providers will be blinded from the actual TV measurements as in routine clinical scenario, and no intervention will be recommended or planned based on the TV measurements.

We will select a convenience sample of 10 patients. All preterm infants born < 32 weeks at Baystate Medical during the 1 year study period will be screened for possible inclusion.

Phase II: We will conduct a randomized control trial to assess feasibility of VTV in the delivery room compared to PLV in preterm infants.

SELECTION OF SUBJECTS

All preterm infants born < 32 weeks at Baystate Medical Center during the 1 year study period will be screened for possible inclusion. With annual delivery of approx.4000 infants, of which 80-100 infant born < 32 weeks gestation, there will be sufficient patient population for the proposed pilot study.

Inclusion Criteria:

- Gestational age < 32 weeks of gestation
- Infant born at Baystate Medical Center
- Requiring intubation and positive pressure ventilation in the delivery room
- Parental Consent

Exclusion criteria:

- Maternal prolonged rupture of membrane > 2 weeks duration
- Known congenital or cardiac abnormalities or discovered in the immediate neonatal period.

Withdrawal/Termination Criteria:

- Withdrawal of parental consent

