PHASE I: No specific withdrawal/termination criteria will be required as this is an observational study to assess feasibility of measuring tidal volume in the DR. Infant will continue to receive routine care as recommended by NRP, even if TV measurements are unsuccessful.

PHASE II: Control Arm: No specific withdrawal/termination criteria will be required, as these infant will continue to receive routine care per NRP recommendations without any study related intervention.

Intervention Arm: If TV cannot be measured or VTV cannot be provided within 60 seconds of initiating PPV via the ETT, the infant will be automatically switched to receiving routine care as recommended by the NRP.

INFORMED CONSENT PROCESS AND TIMING

Who: Parent.

When: "Deferred consent" is being requested after the birth of the child. The study process starts as soon as the baby is born and requires intubation as determined by the clinical team providing resuscitation. We will obtain a deferred consent from the parents only if the baby requires intubation in the delivery room and the TV measurements were obtained. We will approach the parents to use the data that was collected in the delivery room.

Rationale for deferred consent: *In an ideal situation, the consent should be obtained prior to study intervention. However, since the study intervention starts within few seconds to minutes of the baby's birth and it is not*

possible to determine which baby will need intubation in the delivery room, it would be unrealistic to have the opportunity to obtain informed consent we will aim for "deferred consent" process. As this study only present minimal risk to the infants and the device being used is an FDA approved device for use in neonates, a deferred consent is being requested for from the IRB.

How much time to decide: Since study related interventions has already occurred and we are asking parents to give consent for using this information as well as review of electronic medical records parents will have adequate time to make this decision free of any coercion to participate in the study.

Person authorized to obtaining consent: All investigators, program coordinator associated with the study.

SUBJECT FEES: None

REIMBURSEMENT/RENUMERATION FOR PARTICIPTION: None

RISK BENEFIT ASSESSMENT

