Control Arm: Infant will receive pressure regulated breaths, 40-60 breaths/min, PiP of 20-24cm of H₂O as recommended by 2017 Neonatal Resuscitation Program (NRP) guidelines. Reading of the TV will be blinded from the providers as in routine clinical situations

Intervention Arm: Infants in the intervention arm will receive VTV following intubation. Peak inspiratory pressure (PiP) provided via T-piece resuscitator will be visible to the providers, and the provider can regulate the PiP to achieve the desired TV goal (4-6 ml/kg), at a rate of 40-60 breaths/min according to a predefined protocol

The infants will continue to receive respiratory support as assigned by the study arm for the first 48 hours of life, following which they will receive routine VTV and weaning as per standard of care NICU practice.

BLINDING

Phase I: Providers will be blinded from the measured TV during the resuscitation.

Phase II: Due to the providers being aware of ventilation process and the need for change in ventilator settings based on the infant's TV, blood gas, blinding the providers will not be possible. Acknowledging this, we will be blinding the outcome assessment. The individual collecting the data for the two groups and performing the physiologic BPD testing will be blinded on the infant's randomization status. Need for discharge home on oxygen will be assessed by a physician not associated with the study and strict guidelines will be followed for discharge home on oxygen. Provider performing long term outcome assessment will also be blinded from the infant randomization status during the study.

PRIMARY OUTCOME VARIABLE

Phase I: Successful measurement of tidal volume in within 60 seconds of intubation and initiation of PPV.

Phase II: Timing of initiation of VTV will be similar to PLV.

STUDY ENDPOINTS

The study patient will continue in the randomized arm for the first 48 hours of life with ongoing data collection for the first 48 hours after initial neonatal resuscitation. After the first 48 hours, infant will continue standard of care per the NICU providers, with continued data collection for longer term outcomes.

SAMPLE SIZE

Phase I: We will select a convenience sample of 10 successive patients for the initial phase of the study.

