Phase II: We will enroll a total of 30 patients (15 per study group). The sample size was selected to insure sufficient number of patients to estimate variability and effect sizes^{xxi} and to estimate recruitment rates. For example, with 30 patients, the width of the 95% confidence will be about 55% as wide as the standard deviation. This estimate will help develop sample size estimates for future studies.

DATA COLLECTION AND STORAGE

Study data will be collected and managed using a secure, web-based, password protected RedCap (Research Electronic Data Capture) data base^{xxii}. Baseline demographic maternal and infant characteristics, TV, PiP, mean airway pressure, PEEP, FiO₂, resuscitation details, duration of invasive mechanical ventilation, duration of non-invasive respiratory support (non-invasive mechanical ventilation, continuous positive airway pressure), duration of oxygen treatment, home O₂ requirement, BPD incidence and severity along with pulmonary complications will be collected. Standard BPD definition of mild (oxygen use for 28 days), moderate (oxygen need at 36 weeks), or severe (ventilatory support at 36 weeks), along with physiologic BPD testing at 36 weeks will be used to define BPD. This data will also be used prospectively in a future randomized control trial if feasibility study is successful. The research team members and DSMB will have access to the full data set.

DATA ANALYSIS

As the study is designed as a pilot, no formal tests of hypotheses will be conducted^{xxiii}. In Phase I, our goal is to attain skill and competency with using the device, as well as to establish that our measures are reliable and valid. Descriptive statistics will be use to assess the feasibility of measuring TV in the DR. Feasible will be defined as being able to successfully measure the TV in 80% of the infants within 60 seconds of starting PPV via the endotracheal tube.

For Phase II of the pilot project, data analysis will be limited to point estimates (e.g., means and proportions). We will describe the feasibility of using VTV in the DR, and data analysis will be limited to estimating the point estimates (e.g., means and proportions) and variability of ventilatory measures in each group and overall. We will also estimate recruitment and attrition rates, as well as the duration of the consenting process.

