We will use the pilot phase to begin identifying and assessing the frequency of adverse events for developing safety measures. Additionally, the pilot data will be used to estimate effect sizes and variability so that sample size and statistical power may be computed for a later randomized control trial.

Although this study will not be powered to evaluate differences in longer term pulmonary outcomes like BPD, we will still assess for possible trends in difference of BPD and other pulmonary outcomes between the two groups. Being a feasibility study, this study will not be powered to evaluate the safety and other long term outcomes between the two arms, but we will collect and analyze the safety data especially since we will be using the enrolled patient data for the future randomized control trial.

VULNERABLE POPULATION

This study involves studying newborn infants, who are considered vulnerable population. In phase I, the subjects involved in the study will have minimal risks as they will receive standard of care practices and we will only assess our ability to measure the TV in this population. In Phase II, the control arm has minimal risk as they will receive standard of care practices. The intervention arm may potentially have direct benefit as with the information about TV during resuscitation, we can target our PiP for goal TV, thereby minimizing volutrauma and/or atelectotrauma. Thus, overall this study poses none to minimal risk for the study subjects and may potentially benefit the infants in the intervention arm.

For the Phase II the study related interventions will be done only after a written informed parental consent has been obtained.

DATA AND SAFETY MONITORING

Safety data will be monitored closely for all enrolled subjects with special focus on infants randomized to the intervention arm in Phase II. Subjects in the intervention arm, based on the tidal volume generated, the maximum PiP will be limited at 30cm of H₂O, as it would be considered unconventional to require more PiP than 30cm of water in the immediate neonatal phase for longer than 60 seconds duration. If the tidal volume cannot be measure within 60 second, the patients will continue to receive conventional PLV during the time eliminating any potential harm to the patient. We will monitor for development of any pulmonary complication in the enrolled subjects including but not limited to pneumothorax, pneumo-mediastinum, and pulmonary interstitial emphysema.

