- The DR staff including the attending neonatologists, advanced practitioners and respiratory therapists will be trained and will have ample time to feel comfortable about the flow sensor and the Respirationics device prior to starting the study. Our staff currently uses a similar flow sensor device in the NICU and thus we do not anticipate any significant issues pertaining to training.

Subject stopping rules:

- Development of pneumothorax, pneumomediastinum
- PiP requirement >30 cm H₂O pressure for more than 60s
- Persistent low saturation or bradycardia with 60 seconds of optimum VTV

Individual responsible for stopping/modifying the protocol: **[name], MD**, Interim Division Chief along with the IRB will serve as the Safety Monitor for the study. Any SAEs will be reported to the IRB within 48 hours of occurrence.

POTENTIAL PITFALLS AND ALTERNATIVES

Inability to measure small tidal volume: As the *Respironics NM3 monitor* has never been tested to measure TVs in the range of 2-3ml/breath, we potentially run the risk of inability to measure the TV in this range in the extremely low birth weight infants (<500gm). We do plan to measure the TV in a standard test lung after acquisition of the device to ensure accuracy. Alternatively, we may have use the *Dräger Babylog VN500 ventilator* with a flow sensor device to measure TV in the DR. This will be more challenging as having a ventilator in the DR, but is possible to have one stand by, only to measure the TV from its circuit.

Leak from the ETT: Presence of a large leak may pose a significant problem in clinical situations as it makes accurate estimation of TV difficult. We will strictly adhere to the NRP guidelines for endotracheal tube sizes according the patients weight and gestational age and will evaluate both inspiratory and expiratory TV for the study. In situations with a large leak (>50%), we will use the expiratory TV as the marker for delivered TV.

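### Parents are asked for consent only when a tidal volume was obtained, so complete measurement failures leave the Phase I feasibility percentage and bias it upward

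*Combined protocol and SAP*

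**What the plan says.** Under Informed Consent Process and Timing, the protocol requests deferred consent after birth, to be sought "only if the baby requires intubation in the delivery room and the TV measurements were obtained". Its stated purpose is permission to use what was recorded: "We will approach the parents to use the data that was collected in the delivery room". The section carries no phase label. Inclusion Criteria lists "Parental Consent".

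The Phase I primary outcome (Primary Outcome Variable) is "Successful measurement of tidal volume in within 60 seconds of intubation and initiation of PPV". Data Analysis sets the criterion: "Feasible will be defined as being able to successfully measure the TV in 80% of the infants within 60 seconds". The sample is a convenience series of 10 successive patients, analysed descriptively. A further Phase I objective is "To assess the % infants with all equipment ready(including NM3 monitor and flow sensor) in DR to measure TV".

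Potential Pitfalls and Alternatives accepts that measurement may fail altogether. The monitor has not been tested at 2 to 3 ml per breath, and "we potentially run the risk of inability to measure the TV in this range in the extremely low birth weight infants".

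On Phase II consent, Vulnerable Population states: "For the Phase II the study related interventions will be done only after a written informed parental consent has been obtained".

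**The concern.** A feasibility percentage must include the cases in which the procedure failed. Here an infant enters only with consent, and consent is sought only once a TV exists. An infant with equipment not ready, a failed sensor or a breath too small for the monitor has no TV, so is not approached and does not enter. Such an infant is a clear failure on the primary outcome, and the rule removes it.

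The equipment-ready objective is exposed in the same way, because an infant for whom the equipment was never in place has no TV.

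The losses may also be selective. If unreadable small volumes are a cause, the infants removed are mainly the smallest. The Innovation section gives those small volumes as the reason the feasibility study matters. A successful Phase I is also presented there as evidence that consistent volume targeting is possible in the delivery room, so an inflated figure would carry into the case for Phase II.

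**Working it through.** **Nothing to reproduce.** The 80% is a chosen criterion and the 10 patients are a convenience sample. The check is what percentage the consent rule would produce.

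**Inputs from the protocol.** Consent only if a TV was obtained (Informed Consent Process and Timing); consent required for inclusion (Inclusion Criteria); success means TV within 60 seconds (Primary Outcome Variable); criterion 80% (Data Analysis); 10 patients (Sample Size).

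**Assumed input.** The share of infants never measured is not given, so a range is used.

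**Formula.** Among all eligible infants intubated in the delivery room, let p be the share measured within 60 seconds, q the share measured later and m the share never measured, with p + q + m = 1.

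- All infants counted: expected percentage = p.
- Only infants with a TV counted: expected percentage = p/(p + q) = p/(1 − m).

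The inflation factor is 1/(1 − m), and the true rate that reads as 80% is 0.8(1 − m).

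| Never measured, m | Inflation factor | True rate when 80% is reported |
|---|---|---|
| 5% | 1/0.95 = 1.05 | 76% |
| 10% | 1/0.90 = 1.11 | 72% |
| 20% | 1/0.80 = 1.25 | 64% |
| 30% | 1/0.70 = 1.43 | 56% |

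**Chance of meeting the criterion.** With 10 infants, 80% means at least 8 successes. For success rate r this is the binomial tail Σ C(10,k) rᵏ(1 − r)¹⁰⁻ᵏ, summed over k = 8, 9, 10. The restricted column assumes enrolment continues until 10 infants with a TV have been consented.

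| Timely / late / never (assumed) | Rate, all counted | Rate, TV obtained only | P(≥8/10), all counted | P(≥8/10), TV obtained only |
|---|---|---|---|---|
| 85 / 10 / 5 | 85% | 0.85/0.95 = 89.5% | 0.82 | 0.92 |
| 80 / 15 / 5 | 80% | 0.80/0.95 = 84.2% | 0.68 | 0.80 |
| 70 / 10 / 20 | 70% | 0.70/0.80 = 87.5% | 0.38 | 0.88 |
| 60 / 20 / 20 | 60% | 0.60/0.80 = 75.0% | 0.17 | 0.53 |
| 60 / 10 / 30 | 60% | 0.60/0.70 = 85.7% | 0.17 | 0.84 |

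**In counts.** Of 10 successive intubated infants, suppose 3 are never measured and 1 is measured late. Counting all gives 6/10 = 60%, below the criterion. Counting only those with a TV gives 6/7 = 86%, above it.

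**Limits of the effect.** The restricted rate reaches 80% when p/(p + q) ≥ 0.8, that is when q ≤ p/4. It equals 100% only if no measurement is late. If m = 0 there is no bias.

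**The case against.** The strongest reply is that the protocol never defines the denominator, so the consent sentence need not set it.

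- **Screening.** All births under 32 weeks are screened and the 10 patients are successive, so failures could be counted from screening records. However, screening is described only as a step towards possible inclusion, and no rule makes screened or intubated infants the denominator.
- **Unsuccessful measurements.** Withdrawal/Termination Criteria says routine care continues when measurement fails, which could be read as keeping such infants in the study. That sentence gives neither a consent route nor a counting rule.
- **Intent.** The equipment-ready objective would be almost empty if infants without equipment could not enter, which suggests the exclusion was not intended. That may be so, but the written rule still produces it.
- **Phase.** The consent section is unlabelled and speaks of interventions, while Phase I is observational. Vulnerable Population carves out Phase II only, so the rule applies at least to Phase I.
- **Size.** No rate of non-measurement is given, and the largest contrasts need 20% to 30%. The small-volume risk is stated for infants under 500 g, and a test-lung check, staff training and an alternative ventilator sensor are planned. A large leak is not a cause, because expiratory TV is then used. At 5% never measured the shift is about 4 points, which is small beside the exact 95% interval of 44% to 97% for 8 of 10.

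The point on size stands: the magnitude is assumed and may be modest. It does not change the direction, and the planned safeguards do not say how an infant with no TV is counted. A descriptive pilot can still report a biased percentage, and this one is held to an explicit criterion.

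**Conclusion.** The concern holds. The consent rule and the inclusion criterion together condition entry to Phase I on a component of its primary outcome. The expected percentage is p/(1 − m) instead of p, which is too high whenever any eligible infant is never measured. The equipment-ready percentage is exposed to the same selection.

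The size rests on the assumed m: a reported 80% would mean a true rate between 76% (m = 5%) and 56% (m = 30%). The conclusion also assumes that the consent rule is applied as written and that no separate count of unmeasured infants is kept; the protocol provides for none.

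This must be corrected before enrolment, because infants whose parents were never approached may not be recoverable later.

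Separately, the consent section calls prior consent unrealistic, while Vulnerable Population requires written consent before Phase II interventions. These must be reconciled. Phase II percentages for measurable TV and for failure of volume targeting would be biased only if the deferred rule governs there.

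**What to change.** 1. In Informed Consent Process and Timing, delete the condition that a TV was obtained. Approach the parents of every eligible infant intubated in the delivery room.
2. In Data Analysis, define the Phase I denominator as consecutive eligible infants under 32 weeks intubated in the delivery room, whether or not a TV was obtained.
3. Count equipment not ready, no TV, and TV after 60 seconds as failures, and report each separately.
4. With IRB agreement, keep a minimal log of infants whose parents refused or were not approached: intubated, equipment present, TV within 60 seconds yes or no. If the IRB prefers that parents of unmeasured infants not be approached, such a log could supply the counts instead.
5. Reconcile the two consent statements so that one rule applies to Phase II. If consent there follows randomisation, report all randomised infants by arm as far as the IRB permits.

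The cost is protocol wording, an IRB amendment and a few more families. Per 10 infants with a TV, the extra number is 10/(1 − m) − 10, which is 0.5 at m = 5% and 4.3 at m = 30%. The reported feasibility percentage may be less favourable.

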Providing VTV to the VLBW infants is a standard of care practice upon admission to the NICU, with this study we seek to provide more physiologic VTV to the infant immediately after birth without any delay.

Phase I: No risk and no benefit directly to the patient, as this is the observational phase of the study. Information obtained from this phase study may potentially be beneficial by supporting the need for future studies in preterm infants with need for invasive respiratory support.

Phase II: Infants in intervention arm will receive the same routine care with additional information about the TV being delivered to the study infants. The provider's ability to adjust the PiP to provide goal TV may be potentially beneficial for the study infants, as in current DR practice the delivered tidal volume is unknown and infant may be receiving TV out of the set goal range. Infants in the control arm will not have any direct risk or benefit. The only concern would be adding less than 1ml of dead space with the flow sensor, which may or may not be of any clinical significance at all.

UNANTICIPATED PROBLEMS AND SERIOUS ADVERSE EVENT REPORTING

Unanticipated problems and serious adverse events to the subjects related to the study will be reported to the IRB within 48 hours of the occurrence.

RANDOMIZATION

Phase I: No randomization. All infants will receive pressure regulated breaths, 40-60 breaths/min, PiP of 20-24cm of H₂O as recommended by 2017 Neonatal Resuscitation Program (NRP) guidelines. Providers will be blinded from the measured TV during the resuscitation.

Phase II: All infants born <32 weeks will be randomized to one of the study group. Randomization will be via sealed envelope, opened in DR after the decision to intubate is made, with a 1:1 randomization ratio. To keep the gestational age in the two study arm relatively similar, as we are proposing only a small sample size for this current study, randomization will be stratified by gestation age group (Randomization subgroup I: <28 weeks and subgroup II: 28-32 weeks). Infants in both the arms will have a flow sensor at the ETT connected to Respironics NM3 monitor (Philips Healthcare, Eindhoven, Netherlands), to measure breath to breath TV.

INTERVENTION

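### Phase II randomises within gestational-age strata, but the planned arm comparisons and effect-size estimates do not use the stratum

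*Combined protocol and SAP*

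**What the plan says.** RANDOMIZATION sets a 1:1 allocation by sealed envelope, "opened in DR after the decision to intubate is made, with a 1:1 randomization ratio". It states that "randomization will be stratified by gestation age group". The strata are given as "Randomization subgroup I: <28 weeks and subgroup II: 28-32 weeks", and the reason is explicit: "To keep the gestational age in the two study arm relatively similar, as we are proposing only a small sample size". No block size or other restriction within strata is stated.

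SAMPLE SIZE sets 30 infants, 15 per arm, to allow variability, effect sizes and recruitment to be estimated. Its only precision statement is that "with 30 patients, the width of the 95% confidence will be about 55% as wide as the standard deviation".

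DATA ANALYSIS rules out formal tests. For Phase II, "data analysis will be limited to estimating the point estimates (e.g., means and proportions) and variability of ventilatory measures in each group and overall". It adds that effect sizes and variability from the pilot will be used to size a later RCT, and that BPD and other pulmonary outcomes will be examined for trends between arms. Under SPECIFIC AIMS, Phase II Aims 2 and 3 list comparisons between arms of tidal volume, FiO2, airway pressures, blood gases, complications and BPD. Nowhere does the analysis mention the stratum, a summary by stratum or an adjusted contrast.

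**The concern.** The protocol treats gestational age as important enough to control in the design, then drops it from the analysis. Two things follow if the outcome depends on gestational age.

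- **The point estimate.** If one arm has more infants under 28 weeks by chance, the crude arm difference includes part of the gestational-age difference. This matters even in a purely descriptive analysis.
- **The SD handed on.** A crude within-arm SD contains the variation between strata. An RCT that adjusts for gestational age needs the within-stratum SD, which the plan does not produce.

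Effect sizes and variability are the stated products of this pilot, so the plan should define them.

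**Working it through.** **Inputs from the protocol.** 30 infants, 15 per arm, two strata (RANDOMIZATION, SAMPLE SIZE). Expected stratum sizes, outcome means and SDs by stratum, and block size are not given.

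**Assumptions.** Let d be the difference between stratum means in units of the within-stratum SD, and p the share of infants in one stratum. Neither is in the protocol, so a range is shown.

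**1. The plan's own figure.** Read as a 95% interval for one SD with n = 30, the limits are SD × √(29/χ²) on 29 degrees of freedom: 0.796 to 1.344 SD. The width is 1.344 − 0.796 = 0.548 SD, which matches the stated 55%. This figure does not depend on the strata.

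**2. Crude against within-stratum SD.** With the same stratum mix in both arms, the ratio is √(1 + p(1−p)d²), and the ratio of RCT sample sizes is its square. The last column illustrates an RCT with a target difference of 0.5 within-stratum SD, 80% power and two-sided 5%, where the within-stratum SD gives 63 per arm. At p = 0.5:

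| d | SD ratio | n ratio | RCT n per arm using crude SD |
|---|---|---|---|
| 0 | 1.000 | 1.00 | 63 |
| 0.25 | 1.008 | 1.02 | 64 |
| 0.5 | 1.031 | 1.06 | 67 |
| 1 | 1.118 | 1.25 | 79 |
| 1.5 | 1.250 | 1.56 | 99 |

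At p = 0.7 the SD excess is slightly smaller: 2.6% at d = 0.5 and 10.0% at d = 1.

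**3. Chance imbalance without blocking.** Assume 15 infants per stratum and simple randomisation within each. The two arms' shares of infants under 28 weeks then differ by 20 percentage points or more in about 36% of trials. If the arms are held at 15 each but strata are not balanced, the probability is 1 − 2·C(15,7)²/C(30,15) = 0.466, about 47%. A 20-point imbalance shifts the crude arm difference by 0.20 × d: 0.1 within-stratum SD at d = 0.5 and 0.2 at d = 1. Adjustment for stratum removes this shift.

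**4. Cost of adjusting.** If a 95% interval for an arm difference were computed with 15 per arm and balanced strata, its half-width would be t × √(2/15) × SD. At d = 0 this is 0.748 SD crude (28 degrees of freedom) and 0.749 SD adjusted (27), so adjustment costs about 0.2%. At d = 1, in units of the within-stratum SD, it is 0.836 crude against 0.749 adjusted.

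**The case against.** The strongest reply is that this is a descriptive pilot of 30 and that two tempting conclusions go beyond it.

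- **That the planned effect intervals are too wide.** A reader might infer this, but no interval for an arm difference is planned. The only interval mentioned is the sample-size illustration, which reproduces as an interval for an SD. The half-widths in step 4 apply only if intervals are added.
- **That the SD passed to the RCT is too large.** A reader might infer this too, but it holds only if the outcome depends on gestational age and the RCT adjusts for it. The protocol establishes neither. For an unadjusted RCT with the same gestational-age mix, the crude within-arm SD is the right input. Using the residual SD there would give a sample too small by 1 − 1/1.25 = 20% at d = 1.

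Other parts of the reply also stand. At n = 30 the SD carries sampling error of −20% to +34%, more than the stratum effect at d = 1 or below. The larger trial's stated target is BPD, a proportion, to which the SD argument does not apply. Tidal volume is measured per kg and targeted in the intervention arm, and control-arm PiP is set within a range, so the stratum may explain little of these. A single residual SD pools the arms, whereas the protocol expects tidal volume to be variable under PLV and stable under VTV.

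One part does not stand. It may be said that stratification already prevents imbalance. Without blocking or a similar restriction it does not, and none is stated.

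**Conclusion.** The omission is plain on the page: the stratification factor is not carried into the arm comparisons or effect-size estimates, and any chance imbalance in it goes uncorrected. For continuous measures with equal strata, the crude SD exceeds the within-stratum SD by 0%, about 3% or about 12% for stratum differences of 0, 0.5 or 1 within-stratum SD. The matching excess in RCT sample size, 0%, 6% or 25%, arises only if that RCT adjusts for stratum. The true stratum difference is unknown. For a descriptive pilot this is a modest gap, worth closing because the remedy is nearly free and bears on what the pilot is meant to deliver.

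**What to change.** Add to DATA ANALYSIS text such as: *Arm differences in the continuous ventilatory measures will be estimated from a linear model with arm and randomisation stratum. Differences in proportions will be weighted by stratum where cell counts allow. All are descriptive. Crude SDs will be reported for each arm, together with the within-stratum (residual) SD; the later RCT will use the SD that matches its own analysis.*

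Keep the per-arm crude SDs as primary descriptions of variability, because a pooled residual SD would hide a difference in variability between PLV and VTV. State in RANDOMIZATION whether allocation is blocked within strata and, if so, how; the block size can be kept from delivery-room staff.

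The stratum is known at randomisation, so no new data are needed. The model costs one degree of freedom. For proportions such as BPD, equal strata leave 7 or 8 infants per arm and stratum, so stratum-weighted differences may be too sparse to use and should then be replaced by counts by stratum.
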